Official title of study: UCI 14-92 / HS #2015- 1889: Phase IV Study of Daylight Photodynamic Therapy

with Aminolevulinic Acid for Actinic Keratoses

NCT Number: NCT03327831

Date of Document: July 1,2015

Protocol/Methods:

The study was designed prospectively to have 90% power to detect a 50% change in number of AKs. The study was approved by the University of California Institutional Review Board. A total of 30 patients were recruited from July 2015-October 2016 at the University of California, Irvine Department of Dermatology. Two patients were lost to follow up. Study inclusion criteria were age >18 years old with >10 actinic keratoses measuring >3mm each on the face or scalp. Exclusion criteria were history of photosensitive skin disorder, current pregnancy, or use of topical or oral retinoids, imiquimod, ingenol mebutate, fluorouracil, or photosensitizing medications in the past 3 months prior to PDT or during the 6 month study period. Patients were also excluded if the weather was rainy on the intended day of treatment.

Patients were instructed to wash their faces using a washcloth with warm, soapy water for 5 minutes in order to remove excess oil and improve drug penetration and then gently curetted with a 4mm non-disposable curette.

After curettage, the ALA (Kerastick®, DUSA) was applied first as spot treatment to the individual lesions and then as field treatment to the entire treatment area. Following ALA application, an avobenzone-containing chemical sunscreen was applied. The chemical sunscreen was utilized to block ultraviolet light (and possible sunburn from daylight exposure) while allowing wavelengths above 400nm to pass through and activate the PpIX.

After application patients were sent outdoors or home with a handheld luxometer (Suncheck Instruments, Model HS1010) and detailed written instructions. All patients were instructed to begin their daylight exposure within 30 minutes of ALA application and to remain in the daylight for 2 hours. We specifically asked patients to be in a shaded area “where you can see the sky but not the sun.” During daylight exposure, patients recorded pain (scale of 0-10), lux, the weather (raining, cloudy, partly cloudy, sunny) at times 0, 1 hour, and 2 hours, and patient

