satisfaction (not satisfied, slightly satisfied, moderately satisfied, or very satisfied). After daylight exposure all patients were instructed to apply physical sunscreen with titanium or zinc oxide and a wide brimmed hat in order to block visible light and prevent further PPIX activation. The patients were not instructed to wash off the ALA afterward. They were instructed to go indoors for the following 48 hours. All patients were given prophylactic valacyclovir 500 mg BID for 7 days to prevent herpes simplex reactivation and possible eczema herpeticum.

Patients were evaluated and photographed at time 0 days, 3 days, 3 months, and 6 months after treatment and AK counts were performed at 0 days, 3 months, and 6 months. Summary statistics were calculated and a Pearson correlation coefficient test was performed (Stata/IC, Version 15) to assess the relationship between lux received and AK count at 6 months.

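### The lux correlation makes no stated use of the day-0 lesion count and has no robustness check; relate lux to the count relative to day 0 and report a rank correlation beside Pearson

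*Combined protocol and SAP*

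**What the plan says.** The final paragraph of Protocol/Methods reports summary statistics and one named test: "a Pearson correlation coefficient test was performed" "to assess the relationship between lux received and AK count at 6 months". It describes no transformation, rank method, plot, outlier rule or adjustment for the starting count. The same paragraph says that lesions were counted at day 0, 3 months and 6 months, so the starting count is available.

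Earlier in the section:

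- Entry requires ">10 actinic keratoses measuring >3mm each on the face or scalp", with no upper limit.
- Thirty patients were recruited and two were lost to follow-up.
- On lux, "patients recorded pain (scale of 0-10), lux, the weather (raining, cloudy, partly cloudy, sunny) at times 0, 1 hour, and 2 hours". How the three readings become one value per patient is not stated.
- On exposure, "We specifically asked patients to be in a shaded area", and rainy treatment days were excluded.
- The design claim is "90% power to detect a 50% change in number of AKs". It concerns the change in count, not the correlation.

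**The concern.** A patient who starts with 40 lesions and clears most of them can still finish with more than a patient who started with 11 and cleared few. Correlating lux with the 6-month count alone mixes treatment response with starting burden, and starting burden is noise for a question about light dose.

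Pearson's coefficient is also sensitive to a point far out on the lux axis, and it loses power against a rank test when either variable is strongly right-skewed. With about 28 patients, a real relation between light and response could be missed, and the null result could then be read as showing that lux does not matter. This is the only inferential result that the document describes.

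**Working it through.** **Inputs.** From the document: 30 recruited, 2 lost, so n = 28 (assuming that both lack a 6-month count); entry above 10 lesions with no cap; lux recorded three times. Not in the document, so assumed: two-sided alpha of 0.05 and the distributions of lux and counts. All powers below come from simulation at n = 28 and illustrate direction and rough size only.

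**1. The plan's own figure.** For a paired mean change, n = ((z_alpha + z_power) × SD / delta)². With n = 30 and delta = 0.5 of the baseline mean, the SD of change must be 0.5 × √30 / (1.960 + 1.282) = 0.84 of that mean (0.82 with the t distribution). No SD is given, so the 90% can be neither confirmed nor refuted. It does not bear on the correlation.

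**2. What 28 patients can detect.** By Fisher's z, r = tanh((z_alpha + z_power) / √(n − 3)).

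- 80% power: tanh((1.960 + 0.842) / 5) = tanh(0.560) = 0.51.
- 90% power: tanh((1.960 + 1.282) / 5) = tanh(0.648) = 0.57.

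Only a strong correlation is reliably found, so avoidable noise matters.

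**3. Using the day-0 count.** Assumed: day-0 count of 11 plus an overdispersed Poisson with mean 8; negative binomial 6-month count; log-linear lux effect; log-normal lux. Power:

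| Log-SD of lux | Pearson, 6-month count | Spearman, 6-month count | Spearman, fraction of day 0 |
|---|---|---|---|
| 0.3 | 68% | 67% | 74% |
| 0.5 | 63% | 68% | 76% |
| 0.7 | 53% | 68% | 75% |
| 1.0 | 38% | 68% | 74% |

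A separate run at log-SD 0.5 gave Pearson 58% rising to 70% and Spearman 63% rising to 70% when the fraction replaced the count, with Type I error near 5%. The fraction helped both tests in nearly every non-null setting. The gain presumes that the 6-month count scales roughly with the day-0 count.

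**4. One outlying lux value.** With a real log-linear effect at log-SD 0.5, one patient's lux is moved and that patient's count is left alone. Power:

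| Lux of that patient | Pearson | Spearman |
|---|---|---|
| as drawn | 62% | 68% |
| 4 × median | 32% | 61% |
| 8 × median | 7% | 61% |

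A separate run at 4 × median gave Pearson 75% falling to 42% and Spearman 77% falling to 70%. With no true relation, a bright point with an unremarkable count left both tests at 5%. False positives needed a point extreme on both axes: at 5 × median lux and a count of 15 against a mean of 5, Pearson rejected in 65% of runs and Spearman in 7%.

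How likely is such a value? At log-SD 0.5, 4 × median lies ln 4 / 0.5 = 2.77 SD out (upper tail 0.0028), so the chance of at least one in 28 is 1 − 0.9972^28 = 7.5%. For 8 × median the chance is 0.04%, 4% and 41% at log-SD 0.5, 0.7 and 1.0. A misread meter would come on top of this.

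**5. Skew alone.** Power on lux and the unadjusted outcome:

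| Setting | Pearson | Spearman |
|---|---|---|
| Bivariate normal, r = 0.5 | 80% | 74% |
| Log-SD 0.5, count mean 5, k = 5, underlying r = −0.5 | 73% | 74% |
| Log-SD 1.0, k = 5, same r | 58% | 73% |
| Log-SD 1.0, k = 1, same r | 41% | 73% |
| Linear in raw lux, Gaussian error, r = 0.5, log-SD 0.5 | 75% | 63% |
| Linear in raw lux, Gaussian error, r = 0.5, log-SD 1.0 | 62% | 38% |

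Here k is the negative binomial size parameter; smaller k means more skew. Under independence both tests reject at about 5%. Under normality Spearman's asymptotic efficiency is 9/π² = 0.912, worth 0.912 × 28 = 25.5 patients.

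**The case against.** The strongest reply is that nothing in the document shows skew. Patients were asked to sit in shade and rainy days were excluded, so the spread of lux may be narrow. At log-SD 0.2 with a log-linear effect, Pearson and Spearman reach 67% and 64% (k = 10), or 43% and 42% (k = 3). If the outcome is linear in raw lux with Gaussian error, Pearson is better by 12 to 24 points. Three readings per patient would dilute one stray value if they were averaged. That no transformation was used is inferred from silence.

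Much of this stands. A reader might infer that Spearman should replace Pearson at no cost. The documents do not support that: the cost is 4 to 6 points under normality, the rank test measures monotone rather than straight-line association, and its advantage depends on a spread that the document does not give. The Gaussian case is a weak guide for lesion counts bounded at zero, however. With negative binomial counts whose mean is linear in lux, Spearman was equal or better (60% for Pearson and 62% for Spearman at log-SD 0.5; 79% and 96% at 1.0).

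A reader might also infer that one bright reading can by itself create a significant result. It cannot unless that patient's count is extreme too. The real risk is that it hides a true relation, and averaging reduces this only if averaging was done, which is not stated.

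Finally, ranks do not supply the missing test of change in lesions, on which the study was powered. That gap is separate and larger.

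**Conclusion.** The concern holds in a limited form. The only named test makes no stated use of the day-0 count and has no robustness check, at about 28 patients. Two weaknesses do not depend on undocumented skew in the population. Differences in starting count cost about 7 to 12 points of power in the settings shown in which the outcome alone was changed, and one lux value at 4 × median cost Pearson 30 to 33 points against 7 for Spearman. The loss from skew is conditional: none or slightly negative when skew is mild, up to 32 points when lux and counts are both strongly skewed.

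It would be wrong to conclude that the Pearson test is invalid, since its Type I error stays near 5%. All sizes rest on assumed distributions and effects, on 28 complete patients, and on 6-month counts that scale with day-0 counts.

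**What to change.** 1. State how the three readings form one lux value per patient.
2. Relate lux to the 6-month count as a fraction of the day-0 count. A log-link count model with log day-0 count as a covariate is an alternative that does not force proportionality. It targets a different estimand and should not be presented as equivalent.
3. Report Spearman with a bootstrap 95% interval and a scatter plot alongside Pearson, not in place of it.
4. Label these analyses post hoc, because the Pearson test is described as already performed.
5. Do not read a non-significant result as evidence that lux has no effect; about |r| = 0.51 is needed for 80% power.

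The cost is a few lines of text and a few commands, with no new data or patients. The downsides are a small loss of efficiency for Spearman if the data are near normal, a monotone rather than linear estimand, and the reduced weight of a post hoc analysis.

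### The only named test correlates lux with the 6-month AK count and leaves out the day-0 count, so starting burden is mixed with response to light

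*Combined protocol and SAP*

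**What the plan says.** The statistical description is the last sentence of Protocol/Methods: "Summary statistics were calculated and a Pearson correlation coefficient test was performed", its purpose being "to assess the relationship between lux received and AK count at 6 months". No change score, percent reduction or baseline covariate is mentioned, and no other test is named.

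The same paragraph records that "AK counts were performed at 0 days, 3 months, and 6 months", so a baseline value exists for each patient. The first paragraph gives the design target: "The study was designed prospectively to have 90% power to detect a 50% change in number of AKs". Entry was for patients "with >10 actinic keratoses measuring >3mm each on the face or scalp", with no upper limit. Thirty patients were recruited and "Two patients were lost to follow up". Light was observed, not assigned: patients themselves noted "lux, the weather (raining, cloudy, partly cloudy, sunny) at times 0, 1 hour, and 2 hours".

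**The concern.** The count remaining at 6 months is the starting count less what cleared, plus anything new. A correlation of lux with that count therefore mixes how many lesions a patient began with and how well the patient responded. For illustration, a patient going from 60 to 15 lesions has cleared 45/60 = 75%, and one going from 12 to 10 has cleared 2/12 = 17%. The first still scores worse on the outcome used.

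Two things are at stake. Variation in starting burden adds noise that can hide a real relation between light and clearance. And because lux was not randomised, any chance or systematic link between lux and starting burden passes straight into the correlation and can imitate or mask a light effect. The second risk is conditional, since nothing in the documents says the two are related.

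**Working it through.** **The stated power.** The 90% figure cannot be reproduced, because alpha, sidedness, SD, test and target N are not given. For a two-sided 5% test of a 50% mean change (normal approximation), it needs an SD of change, as a fraction of the baseline mean, of 0.5·√n/(1.960 + 1.282). That is 0.5 × 5.292/3.242 = 0.82 at n = 28 and 0.5 × 5.477/3.242 = 0.85 at n = 30. The t-based values are 0.79 and 0.82. The figure concerns change in AKs and says nothing about the lux test.

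**Inputs.** n = 30 − 2 = 28, assuming both lost patients lack a 6-month count and all others have usable lux readings. Let r be the correlation of baseline with 6-month counts, and c the correlation of lux with baseline. The documents give neither, so both are varied. Correlations are shown as magnitudes, two-sided 5%, Fisher z.

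**Power when c = 0.** Without baseline, the smallest correlation detectable with 80% power is tanh(2.80/√25) = 0.508. With baseline as a covariate it is tanh(2.80/√24)·√(1 − r²), on the same unadjusted scale. For a true unadjusted lux correlation of 0.45:

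- Without baseline: atanh(0.45) × 5 = 2.42, and Φ(2.42 − 1.96) = 68%.
- With baseline, r = 0.5: the partial correlation is 0.45/√0.75 = 0.520; atanh(0.520) × √24 = 2.82, and Φ(2.82 − 1.96) = 80%.

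| r | Detectable, no baseline | Detectable, with baseline | Power at 0.45, no baseline | Power at 0.45, with baseline |
|---|---|---|---|---|
| 0 | 0.508 | 0.517 | 68% | 66% |
| 0.2 | 0.508 | 0.506 | 68% | 68% |
| 0.3 | 0.508 | 0.493 | 68% | 71% |
| 0.5 | 0.508 | 0.448 | 68% | 80% |
| 0.7 | 0.508 | 0.369 | 68% | 95% |

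**False positives when light has no effect.** The unadjusted lux correlation is then c·r. With c = 0.3 and r = 0.5 it is 0.15, rejected 11.8% of the time. With c = 0.1 and r = 0.5 it is 0.05, rejected 5.7%.

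**Simulation on counts.** 28 patients, 4,000 runs per setting. Assumed: baseline 11 plus a negative binomial, with mean/SD of 20/4, 25/8 or 36/20; median clearance 65%; between-patient logit SD 0.6; Poisson(1) new lesions; log-lux SD 0.6; light effect 0.6 or 0.4 logit per SD of log-lux. The simulated r was 0.32–0.37, 0.48–0.55 and 0.68–0.75 for the three SDs. Power:

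| Slope | Baseline SD | Pearson as named | Baseline added, untransformed | Log scale, no baseline | Log scale, with baseline |
|---|---|---|---|---|---|
| 0.6 | 4 | 84% | 87% | 88% | 90% |
| 0.6 | 8 | 79% | 88% | 85% | 91% |
| 0.6 | 20 | 54% | 86% | 71% | 94% |
| 0.4 | 4 | 53% | 55% | 58% | 60% |
| 0.4 | 8 | 45% | 59% | 53% | 66% |
| 0.4 | 20 | 27% | 58% | 42% | 69% |

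The part due to baseline alone is columns 4 − 3 (untransformed) or 6 − 5 (log scale): 2–3 points at SD 4, 6–14 at SD 8 and 23–32 at SD 20.

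With no light effect, the named test rejects 4.7–5.1% at c = 0, 6–10% at c = 0.15 and 9–22% at c = 0.3. The log-scale model with baseline stays at about 4–5% throughout.

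A second simulation with different assumptions (50% mean clearance, 3,000 runs) gave 8–34% for the named test at c between ±0.3 and 0.5, against 4–6% for percent change or the baseline-adjusted correlation.

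**The case against.** The case against has six parts.

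- **Reading.** The test is described in one clause, which might be shorthand for change at 6 months. Nothing in the text supports that. The clause names the count, and the unspecified summary statistics, even if they include change, do not alter what was correlated.
- **Timing.** The Methods are in the past tense, so a new model would be a re-analysis, not a pre-specified test. This stands as a matter of labelling, but it does not make the unadjusted correlation easier to interpret.
- **Importance.** The lux test is not stated to be primary or powered, and the before/after AK result is untouched. This stands and limits the severity.
- **Size.** Every magnitude rests on assumed inputs. An open upper limit permits a wide spread of baseline counts but does not show one. At SD 4 most of the 6–7 point total gain comes from the log scale, not from baseline. This stands too.
- **False positives.** They require lux to be related to starting burden. The common shade and 2-hour instructions and the rainy-day exclusion may limit that. The inflation is therefore a conditional risk, not an expected result.
- **Remedy.** A full regression may be more than is needed, since a Spearman correlation of lux with percent reduction came within 2 power points of it in every setting. That is a fair reason to accept the simpler version, not to leave baseline out.

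**Conclusion.** The concern holds and should be fixed. The one named test uses an outcome that is not clearance and is not the quantity the study was designed around, while the baseline count needed to correct this was already collected.

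If lux is unrelated to starting burden, the test is valid at about 5% and the harm is lost precision. In the closed form, adjustment ranges from a loss of under 2 power points (r = 0), through no gain (r = 0.2), to about 13 points (r = 0.5) and 27 points (r = 0.7). If lux and starting burden are related, a spurious association becomes more likely than 5%, by an amount that depends on a correlation the documents do not give. Confidence in the size is moderate at best; confidence in the direction and in the mismatch of outcome is high.

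**What to change.** Replace the Pearson test with one linear regression: log(6-month AK count + 0.5) on log2(lux), with log(baseline count) as covariate. Report the ratio of counts per doubling of lux with its 95% confidence interval. Fix one lux value per patient beforehand, for example the time-weighted mean of the three readings, (L0 + 2·L1 + L2)/4. Add a Spearman correlation of lux with percent reduction from baseline as a sensitivity analysis. State how many patients have both a 6-month count and usable lux readings. If the original correlation has already been seen, label the new analysis as post hoc and show both.

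Using the 3-month count as a repeated outcome is optional; a GEE or count model would need a small-sample correction at 28 patients.

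The cost is a few sentences in the analysis description and a few lines of Stata on data in hand. The covariate uses one degree of freedom, which loses under 2 power points (68% to 66% in the example) if baseline turns out to be uninformative.
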